- The subject becomes pregnant or plans to become pregnant while on study drug.
- Eligibility criteria violation was noted after the subject started study drug, when continuation of the study drug would place the subject at risk. Note: intentional/prospective deviations from the protocol are NOT allowed, see Section 5.9 Protocol Deviations.

- Introduction of prohibited medications or dosages when continuation of the study drug would place the subject at risk.
- Subject is significantly non-compliant with study procedures.
- Worsening vitiligo as defined by an increase of 25% or higher in T-VASI from Baseline beginning at Week 8.

Additional requirements related to abnormal laboratory values and selected AESIs are located in Section [6.2](#).

During the COVID-19 pandemic, it has been necessary to employ mitigation strategies to enable the investigator to ensure subject safety and continuity of care. The investigator should contact the sponsor medical contact before discontinuing a subject from the study for a reason other than "planned per protocol," to ensure all acceptable mitigation steps have been explored.

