## Study Activities Table

Activity	Screening		Period 1							Period 2				PD Visit	30-Day Follow-up Visit/Call		
	Day -35 to Day -1	Day 1	Baseline	Week 2	Day 29	Week 4	Week 8	Week 12	Day 57	Day 85	Day 127	Day 169	Day 197	Week 28	Week 36	Week 44	Week 52
Visit Window			± 3 Days							± 7 Days							
❑ INTERVIEWS & QUESTIONNAIRES																	
Informed consent	✓																
Eligibility criteria	✓	✓															
Medical/surgical history	✓	✓															
Alcohol and nicotine use	✓																
AE assessment	✓	✓	✓	✓	✓	✓	✓	✓	✓	✓	✓	✓	✓	✓	✓	✓	✓
Prior/concomitant therapy	✓	✓	✓	✓	✓	✓	✓	✓	✓	✓	✓	✓	✓	✓	✓	✓	✓
TB risk assessment questionnaire	✓																
Review and document continued compliance with pregnancy avoidance recommendations in the source records with females of childbearing potential	✓	✓	✓	✓	✓	✓	✓	✓	✓	✓	✓	✓	✓	✓	✓	✓	✓
Patient-Reported Outcome																	
VitiQoL, HADS			✓					✓			✓			✓	✓	✓	✓
F-PaGVA, T-PaGVA			✓		✓	✓	✓				✓			✓	✓	✓	✓
DLQI			✓								✓				✓	✓	
VNS, PaGIC-V					✓	✓	✓				✓			✓	✓	✓	

Activity	Screening	Period 1												Period 2				PD Visit	30-Day Follow-up Visit/Call		
		Baseline		Week 2		Week 4		Week 8		Week 12		Week 18		Week 24		Week 28					
		Day 1	Day 15	Day 29	Day 57	Day 85	Day 127	Day 169	Day 197	Day 253	Day 309	Day 365	Day 52								
Visit Window		± 3 Days												± 7 Days							
 EXAMS																					
Physician Assessments: vitiligo history form	✓																				
Physician Assessments: F-VASI, T-VASI	✓	✓	✓	✓	✓	✓	✓	✓	✓	✓	✓	✓	✓	✓	✓	✓	✓				
Physician Assessments: VES		✓	✓	✓	✓	✓	✓	✓	✓	✓	✓	✓	✓	✓	✓	✓	✓				
Physician Assessments: PhGIC-V				✓	✓	✓		✓		✓		✓		✓		✓	✓				
Physician Assessments: F-PhGVA, T-PhGVA		✓		✓	✓	✓			✓		✓		✓		✓	✓	✓				
Physician/Patient Assessments: ICVA		✓							✓					✓	✓	✓	✓				
CXR	✓																				
12-lead ECG	✓													✓	✓	✓	✓				
Height	✓																				
Weight	✓	✓				✓		✓		✓				✓	✓	✓	✓				
Vital signs (blood pressure, heart rate, respiratory rate, body temperature)	✓	✓	✓	✓	✓	✓	✓	✓	✓	✓	✓	✓	✓	✓	✓	✓	✓				
Physical examination including skin examination	✓	✓							✓				✓		✓	✓	✓				
Digital Imaging (performed only at a subset of sites)			✓		✓		✓		✓		✓		✓	✓	✓	✓					
 LOCAL LAB																					
Urine pregnancy test (at Baseline, Week 2, Week 4, and every 4 weeks thereafter)			✓	✓	✓	✓	✓	✓	✓	✓	✓	✓	✓	✓	✓	✓	✓				

Activity	Screening		Period 1							Period 2				PD Visit	30-Day Follow-up Visit/Call

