2.4 Sample Size Determination

Assuming a Week 24 percent change from Baseline in F-VASI of 0% in the placebo arm, a conservative estimate based on a prior study in vitiligo,¹ the planned total sample size of 160 subjects (40 subjects in each upadacitinib group, 40 subjects in total in the placebo groups) will provide more than 90% power to detect the treatment difference of 40% reduction (assuming a standard deviation of 54.8%) in at least 1 upadacitinib group versus placebo using a 2-sided significance level of 0.1 based on the two-sample t-test.

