9.2 Handling of Missing Data

In Period 1, missing data will be imputed using the following methods for the efficacy analyses:

- Mixed-Effect Model Repeat Measurement (MMRM): The repeated measures analysis will be conducted using a mixed model including observed

measurements at all visits. The mixed model includes treatment, visit and treatment-by-visit interaction, and stratification factors (age group [≤ 50 and > 50], Baseline disease severity [T-VASI < 15 and ≥ 15], and status of active vitiligo [Yes/No]) derived from actual values as fixed factors, and Baseline value as a covariate. An unstructured variance covariance matrix will be used. If the model cannot converge, an appropriate covariance structure matrix (e.g., autoregressive (1) or compound symmetry) will be used, and/or the stratification factor of age will not be included in the model. Parameter estimation is based on the assumption of data being missing at random and using the method of restrictive maximum likelihood (REML). MMRM will be the primary approach in the analysis of continuous variables in Period 1.

- Non-Responder Imputation while incorporating Multiple Imputation (MI) to handle missing data due to COVID-19 or any other missing data that can be reasonably assumed to be Missing at Random (NRI-MI): The NRI-MI will categorize any subject who does not have an evaluation during a pre-specified visit window (either due to missing assessment or due to early withdrawal from the study) as a non-responder for the visit. The only exceptions are: 1) when the subject is a responder both before and after the visit window in Period 1, the subject will be categorized as a responder for the visit. 2) missing data due to COVID-19 infection or logistical restriction or any other missing data that can be reasonably assumed to be Missing at Random will be handled by MI. The NRI-MI will be the primary approach in the analyses of categorical variables in Period 1. Random seeds are provided in [Appendix D](#) and more details are provided in [Appendix E](#). NRI-MI is the primary approach to handle missing data for categorical endpoints in Period 1.

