- Multiple Imputation (MI): The MI approach will be used as a sensitivity analysis for the primary efficacy endpoint. Markov Chain Monte Carlo (MCMC) will be first applied to augment data into monotonic missing pattern and PROC MI will be used to generate 30 datasets using the regression method. The variables to be included in the imputation model are: treatment group, stratification factors (age group [≤ 50 and > 50], Baseline disease severity [T-VASI < 15 and ≥ 15], and status of active vitiligo [Yes/No]) derived from actual values, Baseline, and measurements at each visit up to the end of the Period 1. The random seed for MCMC and the random seed for

PROC MI are specified in [Appendix D](#). The imputed post-baseline measurements will be rounded to the same precision as the observed data. The imputed endpoint will be analyzed using each of the 30 datasets using ANCOVA for the primary endpoint. SAS PROC MIANALYZE will be used to generate the final inferences of the difference between upadacitinib group and placebo.

In Period 2, all values collected in the study will be used to summarize the long-term efficacy as observed (AO) in Period 2:

- The AO analysis will not impute values for missing evaluations, and thus a subject who does not have an evaluation at a scheduled visit will not be included in the AO analysis for that visit.

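### The only sensitivity analysis for the primary endpoint omits post-baseline T-VASI, the recorded score that triggers stopping of study drug, so it cannot show whether that dropout route biases the result

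*SAP*

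**What the plan says.** **Stopping rule.** Protocol 5.5 lists, among the reasons to stop study drug at once: "Worsening vitiligo as defined by an increase of 25% or higher in T-VASI from Baseline beginning at Week 8".

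**After stopping.** Protocol 5.6 asks for a PD Visit, preferably within 2 weeks, and a 30-day follow-up visit or call. It describes no continued Period 1 visits. The operations manual was not available for this review.

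**What is recorded.** The Study Activities Table (Protocol Appendix D) puts both scores on one row, "Physician Assessments: F-VASI, T-VASI", so they share a visit schedule.

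**Primary analysis.** The MMRM (SAP 9.2) uses treatment, visit, their interaction, the three stratification factors and Baseline value. "Parameter estimation is based on the assumption of data being missing at random".

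**Sensitivity analysis.** SAP 9.3.3 lists one, MI. Its model in SAP 9.2 reads: "The variables to be included in the imputation model are: treatment group, stratification factors". Baseline and the Period 1 visit measurements follow, without naming the instrument. Appendix E, written for the responder endpoints, specifies the outcome variable's own visits. Its sample code, whose comments also cover plain MI, carries a single outcome series. T-VASI therefore enters only as the Baseline group (below 15, or 15 and above).

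**Estimand.** Treatment policy for treatment discontinuation (SAP 8.0).

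**The concern.** Missing at random protects an estimate only if the observed variables that drive the missingness are in the model. Here the protocol itself names such a variable, post-baseline T-VASI, and the trial records it, yet neither analysis conditions on it. Where T-VASI predicts later F-VASI beyond what F-VASI history, treatment and strata already tell, the Week 24 means of the arms may be biased.

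The more certain problem is that the MI conditions on essentially the same information as the MMRM and makes the same assumption. Agreement between the two would be read as reassurance about missing data, but for this route it carries none. The MMRM estimates also feed the MCP-Mod analysis, where the minimum effective dose is set against a 40% difference from placebo (SAP 9.3.2).

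**Working it through.** **1. The plan's own figure.** SAP 2.4 assumes 40 subjects per comparison group, a "treatment difference of 40% reduction (assuming a standard deviation of 54.8"%), and 2-sided alpha 0.1.

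- SE of the difference = 54.8 × √(2/40) = 12.25.
- Power (normal) = Φ(40/12.25 − 1.645) = Φ(1.62) = 94.7%. The t-test gives 94.4%.
- At least one of three doses, all effective: 99.5%.

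The stated power of more than 90% is reproduced.

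**2. Simulation set-up.** 200,000 subjects per arm, percent change at Weeks 2, 4, 8, 12, 18 and 24, each course a random slope plus visit error.

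- From the SAP: F-VASI SD 54.8 at Week 24; F-VASI mean 0 on placebo and −40 on active.
- Assumed, because the documents are silent: T-VASI SD at Week 24 of 15, 25 or 35; T-VASI mean 0 on placebo and −15 on active; face/body slope correlation 0, 0.3, 0.6 or 0.9; same-visit error correlation 0 or 0.5; error share of Week 24 variance 0.2 or 0.5 for F-VASI and 0.2 for T-VASI.
- Subjects leave after the first visit from Week 8 with T-VASI at +25% or more. All later values are treated as missing, and there is no other dropout.
- Missing F-VASI is predicted by sequential regression on (a) treatment and F-VASI history, or (b) the same plus T-VASI history.

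**3. Results.** Bias is imputed minus true Week 24 mean, in percentage points. Negative means too favourable.

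| T-VASI SD | Meet rule, placebo / active | Placebo bias, (a) | Active bias, (a) | Change in the 40-point benefit, (a) |
|---|---|---|---|---|
| 15 | 2% / 0.2% | −0.9 to +0.3 | −0.1 to 0.0 | −0.8 to +0.3 |
| 25 | 15% / 6% | −5.4 to +1.9 | −2.3 to +0.9 | −3.1 to +1.0 |
| 35 | 29% / 17% | −9.9 to +3.6 | −6.2 to +2.4 | −3.7 to +1.2 |

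Under (b), bias was within about 0.15 points in both arms in every case.

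**4. How it arises.** With T-VASI SD 25, slope correlation 0.6, independent errors and F-VASI error share 0.2, placebo subjects who meet the rule have a true Week 24 mean of +37.5. F-VASI history predicts +21.9. The arm bias is 0.153 × (21.9 − 37.5) = −2.4. The active arm shifts by −1.0, so the difference shrinks by about 1.4.

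**5. When the sign changes.** With slope correlation 0 and same-visit error correlation 0.5 (SD 25, error share 0.2), the true mean is +0.2 and the prediction +12.7, so the bias is 0.153 × 12.5 = +1.9. With slope correlation 0 and independent errors it is about 0.

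**6. Effect on power.** At the largest shrinkage, 40 − 3.7 = 36.3, and Φ(36.3/12.25 − 1.645) = Φ(1.32), about 91%, before any loss of information from missing data. The shift is 3.7/12.25 = 0.3 of a standard error.

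**The case against.** **The direction is not established.** A reader might infer that the placebo mean will be imputed too favourably. The documents give no T-VASI SD, no face/body correlation and no expected rate of meeting the rule. Both scores are physician assessments scheduled at the same visits, so correlated same-visit error is plausible. When that correlation equals the slope correlation and error takes the same share of variance in both scores, T-VASI adds nothing to F-VASI history and the bias vanishes (−0.07 to +0.04 in runs at 0.3/0.3 and 0.5/0.5). This stands: 'may' is as far as the documents go.

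**The effect on the treatment difference is modest.** Active subjects also meet the rule, which partly cancels the placebo shift. In the likelier direction the error works against upadacitinib, in a Phase 2 study without multiplicity control. This stands too.

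**Missing data are not a direct result of the rule.** It stops drug, not study participation, and the plan uses all collected data regardless of discontinuation. The missingness is inferred from Protocol 5.6. The PD Visit may supply one more F-VASI value, and the operations manual could describe more. Hence 'often missing', not 'always'.

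**The repair does not reach the primary analysis.** A reader might infer that it corrects the primary difference and the MCP-Mod inputs. It does not, since both come from the MMRM. Nor does it fully restore missing at random: under treatment policy, off-drug values in the active arms would still be predicted mainly from subjects on drug.

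None of this answers the core point, that the sole sensitivity analysis shares the primary analysis's blind spot for a route the protocol itself creates.

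**Conclusion.** The concern holds as a gap in the sensitivity analysis. Post-baseline T-VASI can trigger stopping of drug, is recorded with F-VASI, and is in neither the MMRM nor, on the most natural reading of SAP 9.2 with Appendix E, the MI. The two analyses cannot disagree in a way that would expose bias from this route.

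The bias may be material or negligible. If T-VASI worsening predicts later F-VASI worsening beyond F-VASI history, which is the likely case, the placebo mean is too favourable and the treatment difference too small. Under the assumed values the placebo bias ran from −9.9 to +3.6 points and the change in the difference from −3.7 to +1.2. If about 2% of placebo subjects meet the rule, the placebo bias stays below 1 point. These ranges rest on assumed SDs, correlations and error shares, and on all F-VASI after the trigger visit being missing. They do not show that the planned primary result will be wrong, or that power falls below the stated level through this shift alone.

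**What to change.** In SAP 9.2, under Multiple Imputation:

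- State that the Baseline and visit measurements are F-VASI.
- Add post-baseline T-VASI (percent change from Baseline at Weeks 2, 4, 8, 12, 18 and 24) as auxiliary variables in both the MCMC step and the regression step.
- Order the variables so that each visit's T-VASI comes before the next visit's F-VASI.
- Report this MI beside the MMRM, described as a check on T-VASI-driven dropout.

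The cost is SAP wording, six more variables in the imputation model and a very small loss of precision: in simulation at 40 per arm, the SD of the estimated difference rose by at most about 2%. No new data are needed. The stopping rule, the primary MMRM and the MCP-Mod inputs stay as they are.

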9.3 Primary Efficacy Endpoint and Analyses

9.3.1 Primary Efficacy Endpoint

The primary endpoint is the percent change from Baseline in F-VASI at Week 24.

The corresponding statistical null hypothesis to the primary endpoint is that there is no difference between any upadacitinib treatment group and placebo, in the LS mean of percent change from Baseline in F-VASI at Week 24.

9.3.2 Main Analysis of Primary Efficacy Endpoint

The primary analysis of the primary efficacy endpoint will be conducted in the ITT_1 Population based on treatment as randomized. The primary analysis is the comparison between upadacitinib and placebo at Week 24 using MMRM, and the corresponding analyses are specified in Section [9.1](#).

The attributes of the estimands corresponding to the primary efficacy endpoint are summarized in [Table 2](#).

Table 2. **Summary of the Estimand Attributes of the Primary Efficacy Endpoint**

Estimand Label	Treatment	Endpoint	Population	Attributes of the Estimand		Statistical Summary
				Intercurrent Events		
Percent change from Baseline in F-VASI at Week 24	Upadacitinib 22 mg QD/ Upadacitinib 11 mg QD/ Upadacitinib 6 mg QD/ Placebo	Percent change from Baseline in F-VASI at Week 24	adult subjects with NSV	For treatment policy strategy, the occurrence of the intercurrent event (treatment discontinuation) is considered irrelevant in defining the treatment effect of interest. Under this strategy, all values for the variable of interest are used regardless of the intercurrent event.		Difference in the percent change from Baseline in F-VASI at Week 24 between each upadacitinib dose and placebo

The second analysis of the primary efficacy endpoint is to test a pre-specified set of dose-response models among upadacitinib dose groups and placebo group at Week 24 using Multiple Comparison Procedure – Modeling (MCP-Mod).

The dose-response relationship among upadacitinib dose groups and the placebo will be characterized for the primary endpoint using MCP-Mod². The percent change from Baseline and standard deviations in each upadacitinib dose groups and placebo based on the primary analysis will be used, and ADDPLAN DF software Version 4.0 will be used to perform the MCP-Mod analyses.

A set of 6 pre-specified standardized candidate dose-response models, as described in [Table 3](#), will be utilized to examine the dose-response relationship. For the primary endpoint, a statistically significant dose-response relationship will be declared if at least one model is identified by the MCP-Mod method to be statistically significant at 2-sided significance level of 0.1. Instead of choosing an optimal dose-response relationship model, a weighted average of the minimum effective dose (MED) (i.e., the recommended MED) across all significant models will be calculated for the MED selection.

1. The MED of each statistically significant model will be determined based on the pre-specified clinical meaningful target of a 40% target difference from placebo.
2. The weighted average of MED across all significant models will be calculated, with the weight W_i of model i calculated using Akaike information criterion (AIC) as:

$$W_i = \frac{\exp(-0.5(AIC_i - \overline{AIC}))}{\sum_{j=1}^J \exp(-0.5(AIC_j - \overline{AIC}))}, \quad \overline{AIC} = \frac{1}{J} \sum_{j=1}^J AIC_j, \quad i = 1, \dots, J,$$

J is the number of significant models.

The rationale for using a weighted average of MED is because selecting a single model as the 'best' representation of observed data and subsequently using it to estimate the MED does not account for uncertainty in model selection. The uncertainty in model selection can be accounted for by averaging estimates of MED over all significant models.

Table 3. Candidate Models

Model	$f(d, \theta)$ $d = \text{dose},$ $\theta = \text{Model Parameters}$	$f^0(d, \theta)$ Standardized Model	Initial Value(s) for Parameter(s)
Linear	$E_0 + \delta d$	d	NA
Exponential	$E_0 + E_1 \left[\exp\left(\frac{d}{\delta}\right) - 1 \right]$	$\exp\left(\frac{d}{\delta}\right) - 1$	$\delta = 44$
Logistic	$E_0 + \frac{E_{max}}{1 + \exp\left(\frac{ED_{50} - d}{\delta}\right)}$	$\frac{1}{1 + \exp\left(\frac{ED_{50} - d}{\delta}\right)}$	$ED_{50} = 4.45, \delta = 5.96$
Emax	$E_0 + \frac{E_{max}d}{ED_{50} + d}$	$\frac{d}{ED_{50} + d}$	$ED_{50} = 2.41$
SigEMax	$E_0 + \frac{E_{max}d^h}{ED_{50} + d^h}$	$\frac{d^h}{ED_{50} + d^h}$	$ED_{50} = 7.28, h = 2.66$
Quadratic	$E_0 + \beta_1 d + \beta_2 d^2$	$d + \frac{\beta_2}{ \beta_1 } d^2$	$\delta = -0.02$

Note: For logistic, Emax, SigEMax, Quadratic models, the initial values for parameters are based on the assumptions that upadacitinib 11 mg will achieve 75% of the maximum efficacy effect, and upadacitinib 22 mg will achieve 95% of the maximum efficacy effect. For exponential model, the initial values for the parameter is solely based on the assumption that upadacitinib 22 mg will achieve 95% of the maximum efficacy effect.

The fitted dose-response curves will be presented graphically for all statistically significant models along with confidence bands.

9.3.3 Sensitivity Analyses of the Primary Efficacy Endpoint

A sensitivity analysis using MI to handle missing data for the primary efficacy endpoint will be performed, as described in Section 9.2.

9.4 Secondary Efficacy Analyses

9.4.1 Main Analyses of Secondary Efficacy Endpoints

Secondary efficacy endpoints in Period 1 will be analyzed by comparing each upadacitinib treatment group with placebo.

Comparisons of the categorical endpoints will be made between each upadacitinib treatment group and placebo using the CMH test, adjusting for the stratification factors derived from actual values under a two-sided significance level of 0.1 for each upadacitinib group, and the corresponding analyses are specified in Section 9.1.

The continuous endpoints will be analyzed using MMRM at a two-sided significance level of 0.1 for each upadacitinib group, and the corresponding analyses are specified in Section 9.1 and Section 9.2.

9.5 Additional Efficacy Analyses

In Period 1, unless otherwise specified, additional efficacy endpoints will be compared between the each upadacitinib treatment group and placebo. The categorical endpoints and continuous endpoints will be analyzed by CMH and MMRM, respectively, and the analyses are specified in Section 9.1 and Section 9.2. Proportion of subjects selecting each of the 16 VitiQoL questions will be summarized for each of the 16 questions by response categories at each visit as observed.

In Period 2, the categorical endpoints will be summarized by treatment groups as observed, and the continuous endpoints will be analyzed as observed using ANCOVA as described in Table 1. The analyses are specified in Section 9.1 and Section 9.2.

In Addition, at the time of the Primary Analysis, additional long-term analysis up to Week 52 will be provided for the below variables among all subjects who may potentially reach to Week 52 by the data cutoff using NRI-MI (categorical variables) or MMRM (continuous variables):

- F-VASI 50, F-VASI 75,
- T-VASI 50,
- Percent change from Baseline in F-VASI,
- Percent change from Baseline in T-VASI

At the time of the final analysis, the above variables will be evaluated up to Week 52 using NRI-MI (categorical variables) or MMRM for the continuous variables.

In addition, for VitiQoL, VNS, DLQI and HADS, analyses will be performed, for up to Week 52, for the following:

- Change from Baseline in VitiQoL question 16 regarding the severity of skin condition.
- Proportion of subjects selecting each of the response categories of VNS
- Change from Baseline in Dermatology Life Quality Index (DLQI) total score
- Achievement of a clinically meaningful improvement in DLQI total score defined as $\Delta \text{DLQI} \geq 4$ (for subjects with $\text{DLQI} \geq 4$ at baseline)
- Achievement of a clinically meaningful improvement in HADS anxiety and depression scores defined as $\Delta \text{HADS} \geq 1.5$ (for subjects with $\text{HADS} \geq 1.5$ at baseline)

